We hypothesize that patient satisfaction with a virtual postoperative visit will be noninferior to patient satisfaction with an in-office postoperative visit

Secondary aims:

- To compare healthcare resource utilization after the postoperative visit up to 12 weeks following urogynecologic surgery between patients receiving in-office versus virtual-video postoperative visits.

We hypothesize that the virtual group will be noninferior to the in-office group based on healthcare resource utilization after the postoperative visit up to 12 weeks following surgery.

- To compare adverse events after the postoperative visit up to 12 weeks following urogynecologic surgery between patients receiving in-office versus virtual-video six-week postoperative visits.

We hypothesize that the virtual group will be noninferior to the in-office group based on adverse events after the postoperative visit up to 12 weeks following surgery.

- To evaluate patient and provider preferences/attitudes toward in-office versus virtual-video postoperative visits

C. RESEARCH PLAN

Overall Study Design

- The study is a randomized controlled noninferiority trial evaluating patient satisfaction with in-office versus virtual-video postoperative visits at six weeks following urogynecologic surgery. We aim to assess whether the intervention of virtual postoperative visit via videoconference technology is noninferior to the standard/traditional in-office postoperative visit for our primary outcome of patient satisfaction. The recruitment period will be 15 months (January 1, 2023 to March 31, 2024). The follow-up period for each participant will be 12 weeks after surgery.

Outcome Measures

- Primary Outcome:
 - Patient satisfaction as measured by the Patient Satisfaction Questionnaire-18 at the 6-week postoperative visit
- Secondary Outcomes:
 - Healthcare resource utilization as measured by patient-initiated phone calls, unscheduled in-person/virtual office visits, emergency room or urgent care visits, and inpatient readmissions after the scheduled postoperative visit up to 12 weeks following surgery
 - Adverse events after the scheduled postoperative visit up to 12 weeks following surgery
 - Patient and provider preferences/attitudes toward virtual or office visits

Eligibility Criteria

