 - Stratified block randomization will be used to ensure that the number of participants is equally distributed among the study groups and stratified by surgery level (major, minor). The allocation sequence will be generated with block size of 4 using computer software. Randomization will be implemented with the REDCap Randomization module. Randomization schedule can only be accessed by a research personnel not directly involved in patient care. The patient's 6-week postoperative visit will be scheduled according to her assigned group.
- Study instruments:
 - Study instruments will be administered at the preoperative visit and the 6-week postoperative visit. The questionnaires for this study include the Patient Preparedness Questionnaire (PPQ), the Patient Satisfaction Questionnaire-18 (PSQ-18), and modified patient and provider preference questionnaires entitled, Patient Postoperative Visit Questionnaire and Provider Postoperative Visit Preference Questionnaire.
 - The PPQ will be administered during the preoperative visit to assess patient knowledge and preparedness for surgery, which has been demonstrated in other studies to impact postoperative satisfaction, perceived complications, and drug utilization.¹⁰⁻¹¹ The PPQ is a 11-item questionnaire scored on a six-point Likert scale and has responses ranging from 1 (strongly agree) to 6 (strongly disagree).⁹ The questionnaire for this study will utilize the same six-point scale with a reversed scoring system, ranging from 1 (strongly disagree) to 6 (strongly agree). Although there are currently no validated measures to assess surgical preparedness in urogynecology, the PPQ has been used in several studies assessing surgical preparedness in women undergoing pelvic organ prolapse and/or stress urinary incontinence.^{8,12} These studies utilized the same cutoff score for question 11 (i.e., an answer of "strongly agree" to the question "overall, I feel prepared for my upcoming surgery") to define meeting criteria for preoperative preparedness.
 - The PSQ-18 will be administered after the 6-week postoperative virtual or in-office visit to assess patient satisfaction with their postoperative visit. The PSQ-18 is a

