will inquire about any concerns the patient has regarding recovery, followed by any unanticipated healthcare encounters at outside facilities. These outside healthcare encounters will be documented by the provider in their Epic note to facilitate data collection by the study investigators. The provider will review key aspects of postoperative care (bowel function, urinary function, presence of vaginal bleeding, dietary status, and ambulatory status), postoperative instructions and precautions, findings and procedures done during surgery, and pathology results (if applicable). The provider will then visually examine surgical sites and document their findings in their Epic note. The provider will inquire about any additional questions from the patient and perform additional evaluation/treatments per standard of care. The PSQ-18 and the Patient Postoperative Visit questionnaire will be administered after this visit. The patient may be contacted for up to two times by a study investigator via phone, text or email within 48 to 72 hours after the visit regarding completion of study questionnaires using a script.

- **Provider Recruitment and Study Procedures**
 - Surgeons and advanced practice providers will be educated about the study during the Urogynecology Section Research Meeting as part of the provider recruitment process.
 - After the six-week virtual or in-office visit, the provider will fill out the Provider Information Sheet and the Provider Postoperative Visit Preference Questionnaire. The provider will complete the questionnaire at the end of the visit. If this is not feasible, the provider will be sent a text reminder for up to two times to their Cleveland Clinic issued phone number within 48 to 72 hours after the visit.

	Preoperative Visit	Day of Surgery	Postoperative Visit (6 weeks)	End of study follow-up (12 weeks after surgery)
Questionnaire: PPQ	X			
Questionnaire: PSQ-18			X	
Questionnaire: Patient Postoperative Visit			X	
Questionnaire: Provider Postoperative Visit Preference			X	
Data collection: Demographic and baseline clinical characteristics	X			
Data collection: Perioperative characteristics		X		
Data collection: Postoperative healthcare resource utilization, adverse events			X	X

D. DATA ANALYSIS PLAN

- Data Collection

- A) Demographic data will include the following:
 - Date of preoperative visit (MM/DD/YYYY)
 - Route of preoperative visit with surgeon (in-office/virtual)
 - MRN
 - Age (years)
 - Race
 - Ethnicity

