- Hospital readmissions prior to 6-week postoperative visit (Y/N); if Y,
 - Total number of hospital readmissions
 - Date of readmission #1
 - Reason/s for readmission
 - Outcome of readmission (discharge, reoperation, other-specify)
 - Hospital length of stay (no. of days)
- Adverse events prior to postoperative visit (Y/N); if Y, specify (urinary tract infection, neurologic injury, hemorrhage/hematoma, blood transfusion, wound infection and cellulitis, seroma, abscess, pyelonephritis, sepsis, vaginal fistula, vaginal dehiscence, deep venous thrombosis, pneumonia, drainage of abscess, delayed gastrointestinal injury, delayed genitourinary injury, ileus, small bowel obstruction, pulmonary embolism, myocardial infarction, cerebrovascular accident and stroke, death, mesh complication, readmission, reoperation)
- D) Twelve-week postoperative data will include the following:
 - End of follow-up (i.e., date marking 6 weeks after the patient's scheduled 6-week postoperative visit) (MM/DD/YYYY)
 - Number of days postop at date above
 - Patient-initiated phone call to surgeon's office during the next six weeks following the scheduled 6-week postoperative visit (Y/N); if Y,
 - Total number of phone calls (No. of occurrences)
 - Date of phone call #1 (MM/DD/YYYY)
 - Reason/s for phone call #1
 - Outcome of phone call (counseling/reassurance, prescription sent, new order placed, new office/virtual appointment scheduled, advised to go to ED/urgent care, provider placed follow-up call to patient the next day, other-specify)
 - Date of phone call #2 (MM/DD/YYYY)
 - Reason/s for phone call #2
 - Outcome of phone call

- Unanticipated outpatient (office/virtual) visits to surgeon's office during the next six weeks following the scheduled 6-week postoperative visit (Y/N); if Y,
 - Total number of outpatient visits including office voiding trials (No. of occurrences)
 - Total number of voiding trial visits (No. of occurrences)
 - Date of outpatient visit #1 (MM/DD/YYYY)
 - Reason/s for outpatient visit
 - Outcome of outpatient visit (counseling/reassurance, prescription sent, new order placed, new office/virtual appointment scheduled, advised to go to ED/urgent care, hospital/direct admission, reoperation, provider/patient to place follow-up call, other-specify)
 - Date of outpatient visit #2 (MM/DD/YYYY)
 - Reason/s for outpatient visit
 - Outcome of outpatient visit

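### Care at outside facilities is asked about only at the 6-week visit, so emergency visits, readmissions and adverse events treated elsewhere between 6 and 12 weeks can be missed

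*Combined protocol and SAP*

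**What the plan says.** All references are to the combined protocol and SAP.

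- **Outcome window.** Under Outcome Measures (section C), utilization includes "inpatient readmissions after the scheduled postoperative visit up to 12 weeks following surgery", and the safety outcome is "Adverse events after the scheduled postoperative visit up to 12 weeks following surgery". Overall Study Design adds: "The follow-up period for each participant will be 12 weeks after surgery".
- **Question about outside care.** Under Postoperative Visit (6 weeks), the provider asks about recovery, "followed by any unanticipated healthcare encounters at outside facilities". Then: "These outside healthcare encounters will be documented by the provider in their Epic note", so that the investigators can collect the data.
- **Instruments.** "Study instruments will be administered at the preoperative visit and the 6-week postoperative visit". None is planned at 12 weeks.
- **Schedule table.** The row "Data collection: Postoperative healthcare resource utilization, adverse events" is marked at both 6 and 12 weeks. The text describes no visit, call, questionnaire or outside-record request for the 12-week mark.
- **12-week fields** (section D, Data Collection, item D). Phone calls are those made to the surgeon's office. Outpatient visits are likewise restricted: "Unanticipated outpatient (office/virtual) visits to surgeon's office during the next six weeks". The emergency or urgent care, readmission and adverse-event fields are not limited to the home institution, and their source is not given.
- **Margins** (Statistical Analysis). 10 percentage points for composite utilization and 25 for composite adverse events, assessed in the same way as the primary outcome, by a two-sided 95% confidence interval.

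**The concern.** The protocol recognises that care given elsewhere may have to be asked about, and it builds that question into the 6-week visit. The answer can only describe the weeks before the visit, while the stated secondary outcomes begin after it. For the weeks that count, an emergency visit, admission or complication handled at another facility belongs in the data by the field definitions but has no described route into them.

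In a noninferiority comparison, missed events are not a conservative error. If the same share of events is lost in both arms, the observed risk difference shrinks while the absolute margin stays where it is, so a worse arm is more likely to pass. At stake is the claim that virtual visits bring no unacceptable excess of later care or complications. The events that can be lost include the more serious ones.

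**Working it through.** **1. Windows side by side.**

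| | Before the 6-week visit | 6-week visit to 12 weeks |
|---|---|---|
| Counts toward the stated secondary outcomes | No | Yes |
| Patient asked about outside care | Yes, by the provider at the visit | No step described |
| Study instrument | Preoperative and 6-week | None |
| Data fields listed | Yes | Yes, source not stated |

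**2. Components exposed.** Phone calls and outpatient visits are by definition contacts with the surgeon's office, so outside care does not remove them. Emergency or urgent care visits, readmissions and adverse events are exposed.

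**3. The plan's own figure.** The documents give no sample size, event rate or capture rate for these outcomes. The only sample size is for the PSQ-18 (margin 5, SD 10, 80% power). At one-sided 0.05, n per arm = 2 × (10/5)² × (1.645 + 0.842)² = 49.5, so 50 per arm, as stated. With 5% attrition, 100/0.95 = 105.3, so 106. I use 50 per arm below.

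**4. Equal under-capture, composite utilization.** Assumptions: the composite is the proportion of patients with any encounter; true rates are 30% in-office and 40% virtual, exactly on the 10-point margin; a fraction s of patients with an event is captured in each arm. Then

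- observed difference = s × (0.40 − 0.30);
- SE = √{[0.30s(1 − 0.30s) + 0.40s(1 − 0.40s)]/50};
- chance of falsely declaring noninferiority = Φ[(0.10 − observed difference)/SE − 1.96].

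| s | Observed rates | Difference | SE | Normal approximation | Exact enumeration |
|---|---|---|---|---|---|
| 1.0 | 30% vs 40% | 10 points | 0.0949 | 2.5% | 2.6% |
| 0.9 | 27% vs 36% | 9 points | 0.0925 | 3.2% | 3.4% |
| 0.8 | 24% vs 32% | 8 points | 0.0894 | 4.1% | 4.5% |

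For s = 0.8: (0.10 − 0.08)/0.0894 − 1.96 = −1.736, and Φ(−1.736) = 4.1%.

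**5. Loss confined to the exposed components.** Suppose 20% of patients in each arm have an encounter that is always captured, and the remaining 10% vs 20% have only outside-prone encounters, captured at 80%. Observed rates are 20 + 8 = 28% and 20 + 16 = 36%; SE = √[(0.28 × 0.72 + 0.36 × 0.64)/50] = 0.0930; Φ(0.02/0.0930 − 1.96) = 4.1%. Overall capture is then 28/30 = 93% in-office and 36/40 = 90% virtual. A modest overall loss has this effect when the excess sits in the exposed components.

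**6. Unequal capture, true rates 30% vs 40%.**

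- 90% in-office, 70% virtual: observed 27% vs 28%; false noninferiority 17.1%.
- 70% in-office, 90% virtual: observed 21% vs 36%; false noninferiority 0.6%.

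**7. Adverse events, 25-point margin.** With assumed true rates of 10% vs 35%, the same formula gives 2.5% at full capture, 5.1% at s = 0.9 and 9.9% at s = 0.8. A true difference on this margin needs a high virtual-arm rate that nothing in the documents supports, so this shows only how sensitive the test is, not what to expect.

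**The case against.** - **Much of the utilization composite cannot be lost this way.** Two of its four components are contacts with the surgeon's office. If the composite is any encounter, a patient is missed only when every encounter was elsewhere. One listed outcome of a phone call is advice to go to emergency or urgent care, so a patient referred on that way is already counted. This stands: a capture of 60% for the whole composite, for example, would mean that 40% of patients with any encounter never contacted the surgeon's office, which nothing in the documents supports. At 95% capture the error is only 2.8%.
- **The direction is not fixed.** This stands, as step 6 shows. A reader might infer that virtual patients are less tied to the local system and so lose more events. The documents do not support that: all participants are patients of one center, and allocation changes the format of a single visit.
- **A reader might compare a shrunken point estimate with the margin.** A true 12-point excess (30% vs 42%) would appear as 9.6 points at 80% capture or 7.2 at 60%, apparently inside the 10-point margin. But the plan tests a confidence limit. With 50 per arm the upper limits are about 9.6 + 1.96 × 9.0 = 27 points and 7.2 + 1.96 × 8.2 = 23 points, and both fail noninferiority.
- **Data collection at 12 weeks is planned, and an unstated source such as shared records might recover some events.** True, so it cannot be said that all outside events will be lost. But no source is named, and the only described question about outside care precedes the window.

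**Conclusion.** The gap is real and narrower than it first looks. As written, the plan has no described way to find emergency or urgent care visits, readmissions and adverse events treated elsewhere between the 6-week visit and 12 weeks. Phone calls, outpatient visits to the surgeon's office and the PSQ-18 primary outcome are untouched.

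The documents do not support saying that the results will be biased toward noninferiority. That direction holds if capture is equal in both arms or lower in the virtual arm; sufficiently better capture in the virtual arm reverses it. The size cannot be derived either, because no event or capture rates are given. Under the assumed 30% vs 40% with 50 per arm, the false-noninferiority rate for composite utilization moves from 2.5% to about 3.2% at 90% overall capture and 4.1% at 80%. This is a worthwhile, inexpensive improvement to two secondary outcomes and does not threaten the trial's main conclusion.

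**What to change.** Send each participant a short form at 12 weeks after surgery by REDCap, text or email, channels the study already uses. It should be identical in both arms and ask about emergency or urgent care visits, admissions and complications at any facility since the 6-week visit. Use it together with chart review for the secondary outcomes, and state which records are searched and how a patient report is reconciled with the chart. Leave the phone-call and outpatient-visit definitions (surgeon's office) unchanged, so that the outcome is not widened.

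The cost is a minor amendment, a few minutes per patient, and modest staff work on reminders and reconciliation. Some patients will not respond, and self-report is unblinded, so response should be reported by arm.

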 - Marital status
 - Distance from home to clinic (miles)
 - Vaginal parity
 - Menopausal state
 - Current tobacco use (Y/N)
 - BMI (kg/m²)
 - Comorbid conditions (MI, CHF, peripheral vascular disease, cerebrovascular disease, dementia, chronic pulmonary disease, connective tissue disease, ulcer disease, mild liver disease, diabetes, diabetes with end organ damage, hemiplegia, moderate or severe renal disease, any tumor without metastasis, leukemia, lymphoma, moderate or severe liver disease, metastatic solid tumor, AIDS)
 - Charlson Comorbidity Index (CCI) score
 - *Calculation for CCI: diabetes with complications, hemiplegia/paraplegia, renal disease, and malignancies, age 60-69 are assigned a score of 2; age 70-79 moderate/severe liver disease is assigned a score of 3; metastatic solid tumour and AIDS/HIV are assigned a score of 6; the remaining comorbidities are assigned a score of 1*
 - Prior prolapse surgery (Y/N; if Y, specify)
 - Prior anti-incontinence surgery (Y/N; if Y, specify)
 - Preoperative prolapse overall stage based on POP-Q exam (0, I, II, III, IV)
 - Preoperative POP-Q points (Aa, Ba, C, GH, PB, TVL, Ap, Bp, D)
 - Preference for text or email reminder communication
 - Preferred mobile phone number or email address
- B) Perioperative data will include the following:
 - Date of surgery (MM/DD/YYYY)
 - Location of OR facility
 - Surgery level (Minor, Major)
 - Surgery type
 - Concomitant procedures
 - Operative time (minutes)
 - Estimated blood loss (ml)
 - Intraoperative complications (bladder injury, ureteral kinking, bowel injury, vascular injury, EBL ≥300 ml, transfusion, conversion to open procedure, other-specify)
 - Hospital length of stay (no. of hours if <24 hours; no. of days if >24 hours)
 - If patient was admitted, was the admission planned (Y/N)

- If N, specify reason for postoperative admission
- Voiding trial results (Pass/Fail)
 - If Fail, select outcome: foley catheter reinserted, patient taught intermittent self-catheterization
- Postoperative prescriptions at discharge (name, dosing, quantity)

○ C) Six-week postoperative data will include the following:

- Date of postoperative visit (MM/DD/YYYY)
- Number of days postop at 6-week visit
- Route of postoperative visit (in-office, virtual)
 - If virtual, was an in-office visit recommended for further evaluation (Y/N); reason for office evaluation (specify)

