- Emergency department or urgent care visits during the next six weeks following the scheduled 6-week postoperative visit (Y/N); if Y,
 - Total number of ED/urgent care visits (No. of occurrences)
 - Date of ED visit #1 (MM/DD/YYYY)
 - Reason/s for ED visit
 - Outcome of ED visit (discharge, readmission, reoperation, other-specify)
 - Date of ED visit #2 (MM/DD/YYYY)
 - Reason/s for ED visit
 - Outcome of ED visit (discharge, readmission, reoperation, other-specify)
- Hospital readmissions during the next six weeks following the scheduled 6-week postoperative visit (Y/N); if Y,
 - Total number of hospital readmissions
 - Date of readmission #1
 - Reason/s for readmission
 - Outcome of readmission (discharge, reoperation, other-specify)
 - Hospital length of stay (no. of days)
- Adverse events during the next six weeks following the scheduled 6-week postoperative visit (Y/N); if Y, specify (urinary tract infection, neurologic injury, hemorrhage/hematoma, blood transfusion, wound infection and cellulitis, seroma, abscess, pyelonephritis, sepsis, vaginal fistula, vaginal dehiscence, deep venous thrombosis, pneumonia, drainage of abscess, delayed gastrointestinal injury, delayed genitourinary injury, ileus, small bowel obstruction, pulmonary embolism, myocardial infarction, cerebrovascular accident and stroke, death, mesh complication, readmission, reoperation)
- Power Analysis and Sample Size Calculation
 - The primary outcome of this study is to compare patient satisfaction between patients scheduled for office versus virtual six-week postoperative visits.
 - A priori sample size calculation determined that 100 participants (50 per group) would allow for 80% power to assess a noninferiority margin of 5 points on the

total PSQ-18, with a SD of 10 and significance level of 0.05. A minimum important difference has not been reported for the PSQ-18; however, previous studies using this tool demonstrated SD for total PSQ-18 score ranging between 2.6 and 11.8 and used a 5-point interval for the noninferiority margin.^{6,13} To account for an anticipated attrition rate of approximately 5%, we aimed to enroll a total of 106 participants (53 per group).

- **Statistical Analysis**

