- Patient satisfaction (PSQ-18) total scores, as well scores in each of the 7 PSQ-18 domains, will be treated as continuous data and checked for normality. Healthcare utilization will be analyzed individually (number of phone calls, number of outpatient visits, number of emergency department or urgent care visits, number of hospital readmissions), as well as a composite of all encounter types. Adverse events will be analyzed independently but also as a composite utilizing the Clavien-Dindo Grading System for surgical complications. Attitudes toward office/virtual visits will be analyzed by comparing proportions of patients and providers who prefer a virtual visit, prefer an office visit, or have no preference.
- All analyses will be conducted using an intention-to-treat principle. Baseline demographic and clinical characteristics will be summarized using descriptive statistics. Normally-distributed continuous measures will be summarized using mean and standard deviation (SD), whereas those showing departure from normality will be summarized using median and interquartile range (IQR). Categorical measures will be summarized using number of participants and percentage. The primary end-point analysis will be designed to test whether patient satisfaction with a virtual postoperative visit is noninferior to an in-person postoperative visit, as determined by the total PSQ-18 at the scheduled postoperative visit. Noninferiority would be shown if the lower limit of the two-sided 95% confidence interval for the between-group mean difference in the primary endpoint (i.e., the difference between the mean PSQ-18 total score in the virtual group minus the mean PSQ-18 total score in the in-office group) is more than -5 points. Similar analyses will be performed for each secondary outcome. The noninferiority margin is defined as 5 points for the PSQ-18 total score and 0.5 points for the PSQ-18 domain scores, 10% absolute for composite healthcare resource utilization, and 25% absolute for composite adverse events. Planned exploratory subgroup analyses of patient satisfaction, healthcare resource utilization and adverse events based on surgery level will be additionally performed.
- All statistical analyses will be performed using JMP Pro version 17.0 software (SAS Institute, Cary, NC).
- Data will be managed in REDCap. Statistical support will be provided by the Cleveland Clinic Quantitative Health Sciences.

E. PRIVACY AND CONFIDENTIALITY

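### Both adverse-event fields are closed 25-item lists with no 'other' entry and no urinary retention item, so unlisted outpatient complications have no stated route into the safety composite

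*Combined protocol and SAP*

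**What the plan says.** Section D, Data Collection, has two adverse-event fields. The six-week field (part C) begins "Adverse events prior to postoperative visit (Y/N); if Y, specify (urinary tract infection, neurologic injury, hemorrhage/hematoma". The twelve-week field (part D) begins "Adverse events during the next six weeks following the scheduled 6-week postoperative visit (Y/N); if Y, specify (urinary tract infection". Both run through the same 25 items and end with "cerebrovascular accident and stroke, death, mesh complication, readmission, reoperation", after which the bracket closes. Neither has an open entry. The nearest items to urinary retention are urinary tract infection and delayed genitourinary injury.

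Other fields in the same section do have an open entry. Part B has "Intraoperative complications (bladder injury, ureteral kinking, bowel injury, vascular injury, EBL ≥300 ml, transfusion, conversion to open procedure, other-specify". Parts C and D have, for example, "Outcome of ED visit (discharge, readmission, reoperation, other-specify", and the outcome fields for calls, outpatient visits and readmissions are built the same way.

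The plan does follow voiding. Part B records the voiding trial result and how a failed trial was handled. Parts C and D count voiding-trial visits before and after the 6-week visit, but as a subset of outpatient visits.

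Under Statistical Analysis, adverse events are analysed individually and "also as a composite utilizing the Clavien-Dindo Grading System for surgical complications", with a noninferiority margin of 25% absolute. Outpatient visits belong to healthcare utilization, with a margin of 10% absolute. Section B places the adverse-event hypothesis after the postoperative visit, up to 12 weeks. Section G sends any adverse event to the IRB and keeps all events in a study binder.

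**The concern.** The field that feeds a safety hypothesis lacks the open entry that its neighbours have. The study population includes mid-urethral sling and prolapse repair, and the plan itself treats voiding problems as worth tracking, yet they have no adverse-event item. An abstractor who follows the form would answer 'no' for a patient with late retention managed as an outpatient, if she had no listed event. Such a patient is absent from the composite in either arm. If these patients were more numerous after virtual visits, the composite would understate the difference, and the error would favour the noninferiority claim.

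**Working it through.** **The lists compared**

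| Field | Open entry? | Retention/voiding named? | Feeds |
|---|---|---|---|
| Intraoperative complications (part B) | yes | no | perioperative description |
| Call, visit, ED and readmission outcomes (parts C, D) | yes | voiding-trial visits counted | utilization |
| Adverse events before the 6-week visit (part C) | no | no | adverse events |
| Adverse events in the six weeks after it (part D) | no | no | adverse-event composite |
| Section G log | any event | not itemised | IRB and binder; no stated link to the analysis |

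Counting the items in the part D list, from urinary tract infection to reoperation, gives 25.

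An unlisted event reaches the composite only if it leads to readmission or reoperation, because those two are on the list. Otherwise no text carries it there. Section G's own example, a visit missed because of technology, is also an adverse event with no entry on the form.

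**How large the effect could be**

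The plan gives no adverse-event rate and no power figure for this outcome, so there is no stated result to reproduce. Inputs from the plan are 50 per group, the two-sided 95% interval and the 25-point margin. Assumptions are that the composite is the proportion of patients with at least one event, that listed and unlisted events fall in different patients, and the rates themselves. Higher is worse, so the upper limit for virtual minus office is the one to compare with the margin:

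Upper limit = (pV − pO) + 1.96 × √[pV(1 − pV)/50 + pO(1 − pO)/50]

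- Listed events only, 10% in each arm: 0 + 1.96 × √(2 × 0.09/50) = 1.96 × 0.060 = +11.8 points.
- Adding unlisted events, 15% virtual and 5% office, gives 25% versus 15%: 0.10 + 1.96 × √[(0.1875 + 0.1275)/50] = 0.10 + 1.96 × 0.0794 = +25.6 points.

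| Listed, each arm | Unlisted, virtual / office | All events, virtual / office | Upper limit, listed only | Upper limit, all |
|---|---|---|---|---|
| 10% | 5% / 5% | 15% / 15% | +11.8 | +14.0 |
| 10% | 10% / 5% | 20% / 15% | +11.8 | +19.9 |
| 10% | 10% / 4% | 20% / 14% | +11.8 | +20.7 |
| 10% | 15% / 5% | 25% / 15% | +11.8 | +25.6 |
| 10% | 16% / 4% | 26% / 14% | +11.8 | +27.5 |
| 5% | 15% / 5% | 20% / 10% | +8.5 | +23.9 |
| 20% | 15% / 5% | 35% / 25% | +15.7 | +27.9 |

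The chance of showing noninferiority is Φ[(0.25 − d)/SE − 1.96], where d is the true difference and SE the square-root term above. With listed events at 10% per arm:

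- listed only: Φ(0.25/0.060 − 1.96) = 98.6%
- with unlisted events of 5% / 5%: 93.8%
- with 10% / 5%: 75.1%
- with 15% / 5%: Φ(0.15/0.0794 − 1.96) = 47.2%

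Even equal omission shortens the interval at these rates (+11.8 against +14.0), but it does not change the conclusion.

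**The case against.** The strongest reply is that little is truly lost.

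- **The list is not blind to what an examination finds.** It names wound infection, seroma, abscess, hematoma, fistula, dehiscence and mesh complication. This stands. A reader might infer that the complications a virtual visit could miss are left out of the comparison; the list does not support that. Only unlisted ones are at risk.
- **The events remain in the data.** An unplanned visit to the surgeon's office is recorded with reason and outcome, voiding-trial visits are counted through the twelve-week follow-up, and utilization has the tighter margin. This also stands, but Statistical Analysis treats these as utilization and nothing carries them into the adverse-event composite.
- **Section G records everything.** True, but no text links that log to the analysed field.
- **The 6-week checklist proves nothing here.** "The provider will review key aspects of postoperative care (bowel function, urinary function, presence of vaginal bleeding, dietary status, and ambulatory status" describes what happens at the visit, whereas the hypothesis concerns the period after it, and abnormal examination findings can be specified in part C. This stands, and the point does not rest on the checklist.
- **Grading can be done at analysis.** A reader might infer that the composite cannot be graded because the field has no grade or treatment. The documents do not show that: several listed items are themselves treatments or consequences, and encounter outcomes record prescriptions, orders, admissions and reoperations. How grades are assigned is unstated detail, not a shown defect.
- **Some candidate events are a matter of definition.** Whether pain, bowel symptoms or recurrence count as surgical complications is for the investigators to decide, so an open entry needs a threshold.

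**Conclusion.** The gap is real and narrow. Both analysed fields are closed lists without an open entry or a retention/voiding item, and unlisted complications that lead to neither readmission nor reoperation have no stated route into the composite. Events are under-counted in both arms.

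A reader might go further and say that the safety result is biased toward noninferiority. The documents do not support that as a general statement. It holds only if unlisted events are more common after virtual visits, and no rates are given. At the assumed rates, a 6-point excess (10% versus 4%) on top of 10% listed events leaves the upper limit at +20.7, inside the margin. A 10-point excess (15% versus 5%) crosses it at listed rates of 10% or 20% per arm (+25.6, +27.9) but not at 5% (+23.9). The conclusion would change only if unlisted events were fairly common and unequal. This is a worthwhile, cheap improvement to a secondary safety outcome, and it does not touch the primary analysis.

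**What to change.** In both adverse-event fields (section D, parts C and D), add 'urinary retention/voiding dysfunction' and an 'other-specify' entry. Under Statistical Analysis, state that every such entry meeting the Clavien-Dindo definition of a complication enters the composite, write that definition into the plan so that trivial entries are screened the same way in both arms, and count each patient once. Name the recorded reasons for calls, visits, ED attendances and readmissions, and the section G log, as sources for completing the fields.

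The cost is a few REDCap fields and slightly longer chart abstraction; most of the source information is already collected. Recorded event rates will rise in both arms, which widens the interval somewhat at the rates considered here. Patient care is unaffected.
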